3 HYPOTHESIS TESTING

3.1 STATISTICAL HYPOTHESES

This being an observational and exploratory study, no hypothesis has been established.

PFIZER CONFIDENTIAL

3.2 STATISTICAL DECISION RULES

The statistical significance value is set to $p<0.05$. The SAS statistical software version 9.3 or later (SAS Institute Inc., Cary, NC, USA) will be used.

4 ANALYSIS POPULATION

4.1 FULL ANALYSIS SET

Since it is an observational and exploratory study, the number of subjects included will not be pre-determined, although a sample of close to 90 cases is envisaged in about 50 Spanish sites; taking the case collection period into account.

Any number of patients that meet the inclusion criteria and no exclusion criteria may be recruited at the site.

Any patient who meets the inclusion criteria and who does not meet any of the exclusion criteria and has received treatment with Sunitinib prior to participation in the registry will be considered evaluable.

4.1.1. Inclusion Criteria

Patients must meet all the inclusion criteria below to be eligible for inclusion in the study:

[figure not shown]
1. Patients aged 18 years or older who have been treated for a metastatic renal carcinoma with first-line sunitinib in (prior cytokine treatment is admitted) between 2007 and October 30, 2018 and have obtained, as best response to treatment, total disease remission in the opinion of the treating physician from the clinical, radiological and/or macroscopic standpoint. This response must have been achieved through two possible strategies:
 - a. Systemic treatment with Sunitinib alone.
 - b. Treatment with Sunitinib and subsequent local treatment for one or several residual lesions that have not responded to the drug (traditional surgery, radiotherapy, SBRT (Stereotactic Body Radiation Therapy)).
2. The duration of the CR must have been confirmed by at least 2 consecutive imaging tests with no limit on the duration of this response. Patients with subsequent progression may be included in this registry.
3. Patients of any risk group.
4. Tumours of any histology.

4.1.2. Exclusion Criteria

Patients who meet any of the following criteria will not be included in the study:

1. Patients treated with another drug other than Sunitinib.
2. Patients without radiology reports that substantiate the CR.

PFIZER CONFIDENTIAL

3. Patients without a record of the dose and regimen of Sunitinib.
4. Patients who achieved complete remission after October 30, 2018.

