8.2.1. Inclusion Criteria

Patients must meet all the inclusion criteria described below to be eligible for the study:

1. Patients who are 18 year-old or over who have been treated for metastatic renal cell carcinoma with sunitinib as first-line treatment (treatment with prior cytokine therapy is accepted) between 2007 and 30 October 2018 and who have obtained as a best treatment response the total remission of the disease in the opinion of the doctor in charge from a clinical, radiological and/or macroscopic point of view. This response must have been reached through two possible strategies:
 - A) Systemic treatment with sunitinib alone.
 - B) Treatment with sunitinib and subsequent local treatment for one or more residual lesions that have not responded to the drug (traditional surgery, radiotherapy, SBRT (*Stereotactic Body Radiation Therapy*)).
2. The duration of CR must have been confirmed with at least 2 consecutive imaging tests, without having a limit in the duration of this response. Although the patient had progressed subsequently, he/she may be included in this registry.
3. Patients from any risk group
4. Tumours of any histology

The doctor responsible for the patient, in the event that he/she continues to attend routine reviews at the hospital, undertakes to send the patient a privacy alert according to the new EU legislation on personal data: regulation 2016/679 of the European parliament.

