- *In cases of discontinuation of systemic treatment after a period of treatment with maintained CR, the reason for the decision and the patient's participation in this decision (whether the patient was consulted, whether it was at the patient's request or the investigator's decision).*
- *Pharmacological group by mechanism of action used in patients in the second line after disease progression: another TKI, treatment with a drug acting on the immune system.*

Exploratory analysis:

[figure not shown]
Baseline neutrophil/leukocyte ratio and evolution of the neutrophil/lymphocyte ratio throughout treatment; at 4-6 weeks, 3 months, 6 months, 9 months, 12 months and then every 6 months in the available analyses close to these dates.

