- 2) End date and reason
- 3) Date of progression
- 4) Date of and reason for death
- 5) Post-Sunitinib treatments (another TKI, mTOR, immunotherapy)

The following aspects will be assessed using the variables collected:

- **Time from nephrectomy to the start of systemic treatment:** defined as the time interval from the day of the nephrectomy to the day treatment with Sunitinib started.
- **Time to CR:** defined as the time interval from the day treatment with Sunitinib started until the day the complete response is documented in the first CT scan without lesions.
- **Duration of treatment with Sunitinib once CR is reached:** defined as the time interval from the day on which the complete response is documented until the day that the definitive discontinuation of the treatment is confirmed, either at the patient's own decision or at the doctor's decision.
- **Time to progression (TTP):** defined as the time interval from the day on which the complete response is documented until the first day that objective tumour progression, if any, is observed.
- **Time to change of treatment:** in patients who continue treatment with Sunitinib once the lesions have disappeared, it is defined as the time interval from the day on which the complete response is documented until the first day on which the change of treatment due to unacceptable toxicity is documented, as applicable.
- **Time to death:** defined as the time interval from the day on which the

Pfizer Confidential

complete response is documented to the day on which death from any cause is documented, if it occurs.

- **Duration of complete response (DOR):** defined as the time interval from the date on which the complete response to Sunitinib is identified until the date of the CT scan conforming tumour progression, the change of treatment due to unacceptable toxicity, death from any cause or until the date of the last follow-up at the close of the study. It represents the time that the patient survives without signs of disease.

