Time on treatment with Sunitinib once CR is reached	Treatment data (covariate)	Treatment data
Local treatment techniques of residual lesions	Secondary objective	Treatment data
PA (pathological anatomy) of the metastasectomy: histology and degree of necrosis	Disease data (covariate)	Disease data
Highest grade of adverse events related to the treatment with Sunitinib	Secondary objective	Treatment data
Serious adverse events (SAEs) during treatment with Sunitinib	Secondary objective	Treatment data
Pharmacological group of second-line treatment after disease progression after a period of time in CR (TKI, mTOR, Immunotherapy)	Secondary objective	Treatment data
Causes of death	Disease data (covariate)	Disease data

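### Exclusion 1 bars any drug other than sunitinib without a time limit, contradicting the criteria that admit prior cytokines and later progression and the second-line objective

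*SAP*

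**What the plan says.** Exclusion 1 is "Patients treated with another drug other than Sunitinib" (SAP 4.1.2). Protocol 8.2.2 has the same rule, and SAP 7.2.1 lists it again as a reason for non-evaluability. None of the three gives a period, a line of therapy or an indication. SAP 4.1 counts a patient as evaluable only if no exclusion criterion is met, so the rule acts both when sites select cases and when the analysis set is formed.

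Other parts of the same documents point the other way:
- Inclusion 1 allows earlier cytokines: "treatment with prior cytokine therapy is accepted" (Protocol 8.2.1) and "prior cytokine treatment is admitted" (SAP 4.1.1). SAP 7.2.1 repeats this allowance in the list that carries the unqualified exclusion.
- Inclusion 2 states: "Patients with subsequent progression may be included in this registry" (SAP 4.1.1; Protocol 8.2.1 agrees).
- A secondary objective is "Pharmacological group by mechanism of action used in patients in the second line after disease progression" (SAP 2.2; also Protocol 7.2). The drug classes (another TKI, mTOR, immunotherapy) are collected under SAP 5, listed in SAP 5.4 and reported under SAP 7.2.3 and 7.2.4.

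Duration of CR runs "until the date of the CT scan conforming tumour progression", or to a treatment change for toxicity, death or last follow-up (SAP 5). PFS from CR also ends at progression (SAP 7.2.4).

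**The concern.** Eligibility requires every inclusion criterion and no exclusion criterion, so an inclusion does not override an exclusion, and nothing says which text prevails. About 50 sites will select cases from charts in which later drugs are already visible. A site that follows exclusion 1 to the letter leaves out a relapsed patient who went on to another TKI, an mTOR inhibitor or immunotherapy. A site that follows inclusion 2 enters the same patient. A patient who is never entered does not appear in the non-evaluable table of SAP 7.2.1, so the difference would be invisible at analysis.

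Under the literal reading, inclusion depends on a treatment given after the event that ends CR. Removing events this way while keeping patients still in CR pushes the Kaplan-Meier curves for CR duration and PFS from CR upward. These curves feed the recommendations the registry is meant to produce. The second-line table would also lose the patients it is meant to describe.

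**Working it through.** There is no plan figure to reproduce. The size of about 90 cases is a feasibility estimate, and Protocol 8.5 says no sample size calculation is needed. The check is a count followed by an illustration.

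**Count from the cited Czech registry (SAP 2, Protocol 6).** Of 30 patients who stopped treatment after CR, 14 progressed. Of those 14, 12 had second-line treatment, 4 of them with the same drug. If that drug was sunitinib, these 4 do not meet exclusion 1.
- Removed by a literal reading: 12 - 4 = 8, and 8/14 = 57% of relapsed patients.
- Kept: 4 re-treated + 2 without second line = 6, and 6/14 = 43%.
- Apparent relapse share: from 14/30 = 47% to 6/(30 - 8) = 6/22 = 27%.

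**Effect on the median.** Let relapse times be exponential with rate λ = ln 2/median, density f and survival S. Let G(t) be the probability of still being under follow-up at t, and let a share p of patients with an observed relapse be deleted. Among those kept, the hazard that Kaplan-Meier estimates is

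h*(t) = (1 - p) f(t)G(t) / [S(t)G(t) - p ∫ₜ f(u)G(u)du],

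and the apparent median is the time at which the integral of h* reaches ln 2. The true medians tried are two the documents cite: 27.6 months (Czech registry, PFS from CR) and 7.9 months (single-hospital series, TKI alone, CR to relapse). The follow-up patterns are assumptions.

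| True median | Follow-up (uniform) | p = 0 | p = 25% | p = 57% | Patients removed at p = 57% |
|---|---|---|---|---|---|
| 27.6 | 4-130 months | 27.6 | 30.6 | 40.1 | 41% |
| 27.6 | 6-60 months | 27.6 | 33.2 | 52.4 | 30% |
| 7.9 | 4-130 months | 7.9 | 8.1 | 8.8 | 53% |
| 7.9 | 6-60 months | 7.9 | 8.4 | 9.8 | 50% |

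The 25% column stands in for only some sites reading the rule literally.

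**Hand check.** With exponential censoring and event fraction q, h* is constant and the apparent median is the true median × (1 - pq)/(1 - p). With q = 14/30 and p = 8/14, the factor is (22/30)/(6/14) = 1.71. This gives 27.6 × 1.71 = 47.2 months and 7.9 × 1.71 = 13.5 months. The first lies inside the 40-52 range. The second is above 9.8, so the size for short durations depends strongly on the censoring pattern.

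**Prior cytokines.** Removing these patients contradicts inclusion 1. Nothing in the documents gives their share or a direction of effect on CR duration, so no bias is computed.

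**The case against.** The strongest reply is that the plan's intention is clear from context. Prior cytokines are accepted repeatedly, including in the SAP 7.2.1 list itself. Later progression is expressly allowed, and second-line drugs are collected and tabulated. Read as a whole, exclusion 1 most naturally means a first-line drug other than sunitinib. This stands as an account of intent, and it makes the bias hypothetical. It does not remove the defect: the wording still says something else in three places, one of which governs the analysis set.

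A reader might infer that relapsed patients drop out and that CR duration will be inflated. The documents do not support that. No text directs their removal, and even a literal reading keeps those with no second line or with sunitinib again (6 of 14 in the cited registry).

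A reader might also take 12/14 as the share removed. With follow-up of 4-130 months this gives a median of about 99 months in place of 27.6, and about 12 in place of 7.9. It overlooks the 4 patients re-treated with the same drug.

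Two limits on the inputs also stand. The 27.6 months counts deaths as well as relapses, and patients who die without relapse receive no second line, so treating every event as a relapse overstates the effect. The 8/14 comes only from patients who stopped treatment in CR, in a cohort with mixed drugs.

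**Conclusion.** Exclusion 1 is wrong as written. It is an internal inconsistency, not a design choice. Followed to the letter, it removes patients whom inclusions 1 and 2 admit and whom the second-line objective needs, and sites could enrol different populations.

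The upward bias in CR duration and PFS from CR is conditional on literal application. Its direction is the same in every scenario tried, but its size is not settled. With 57% of relapsed patients removed and uniform follow-up, it ranges from about one month (7.9 to 8.8) to nearly double (27.6 to 52). With 25% removed, 27.6 becomes about 31 to 33 and 7.9 about 8.1 to 8.4. These figures rest on exponential relapse times, the assumed follow-up patterns, re-treatment having been with sunitinib, and transfer of the Czech share to this registry. The documents do not give this registry's share of second-line or prior-cytokine patients.

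**What to change.** Reword exclusion 1 identically in Protocol 8.2.2, SAP 4.1.2 and SAP 7.2.1 so that it agrees with the inclusion criteria and the second-line objective. Suggested text: patients who received a systemic anticancer drug other than sunitinib (except prior cytokines) before or during the first-line sunitinib course in which CR was obtained. Add that a drug started after that course ended, whether before or after relapse, does not exclude the patient. The second sentence is needed so that a drug begun after sunitinib stopped, but while the patient was still in CR, is not left open.

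The cost is a short rewording of both documents, submitted as a protocol amendment with prospective ethics committee approval (Protocol 9.4). No new data are needed.

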STUDY TITLE:

REGISTRY OF COMPLETE RESPONSES TO SUNITINIB IN SPANISH PATIENTS WITH METASTATIC RENAL CELL CARCINOMA (ATILA STUDY)

PROTOCOL CODE: A6181227

COORDINATING INVESTIGATOR:

The scientific coordinator will be responsible for maintaining the methodological rigour of the study, both in the design phase and in the evaluation of results and writing of the final report. He/she will guarantee the ethical conduct of the study, maintaining the scientific support for all participating doctors until the publication of the study results:

[name]
PPD [REDACTED]
[REDACTED]
[REDACTED]

STUDY SITES:

It is initially considered optimal to include patients in the Medical Oncology Departments of approximately fifty Spanish sites (see “investigators list”).

IEC ASSESSING THE STUDY

PFIZER CONFIDENTIAL

This protocol has been evaluated in the PPD
, Spain.

PRIMARY STUDY OBJECTIVES:

To describe complete responses in daily clinical practice in Spain between June 2007 - 30 October 2018, such as: the documented disappearance of all lesions of metastatic renal cell carcinoma according to the investigator's criteria in at least 2 consecutive CT scans.

To look for associations between CR from a macroscopic point of view and the baseline characteristics of both the patient and the tumour, such as:

- Demographic data (age at the start of treatment)
- Previous nephrectomy
- Classification of the risk group according to Motzer and/or Heng criteria and the association between each prognostic variable, such as: baseline patient status, time from nephrectomy to systemic treatment start, presence of anaemia, corrected calcium, LDH (Lactate Dehydrogenase) levels, neutrophil levels and platelet levels.
- Tumour data: histology, Fuhrman grade, presence of tumour necrosis and number and location of metastases (organs involved).

DESIGN

Post-authorisation, observational, retrospective, multicentre study.

STUDY CONDITION

Advanced/metastatic renal cell carcinoma

STUDY POPULATION AND TOTAL NUMBER OF SUBJECTS

Patients over 18 year-old with advanced carcinoma with a renal cell component who have received sunitinib as a first-line treatment according to drug indication and who have achieved CR according to the responsible medical team criteria, will be included.

During the study recruitment period, the participating sites may include all patients who fulfil the inclusion criteria and none of the exclusion criteria of the protocol.

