- Time on treatment with Sunitinib until complete remission of lesions, calculated as the difference between treatment start date and CR confirmation date (2nd CT scan).
- Duration of complete remission (DOR)
- Progression-free survival (PFS) or time from remission to disease progression, change of treatment due to unacceptable toxicity or death. It will be calculated as the time elapsed from the RC confirmation date (2nd CT scan) until the date of progression/death or change of treatment for unacceptable toxicity, as applicable, or else it will be censored on the date of the last patient follow-up.

Taking into account the asymmetry normally observed in the distribution of survival times and that follow-up periods may be uneven (different study entry date), the Kaplan-Meier method will be used to estimate the median time to CR together with its 95% confidence interval. The median will indicate when complete remission of the disease occurred in 50% of patients.

In order to find associations between time to CR and the baseline features of both patient and tumour, a log-rank test will be used for comparison between groups and the determination of the statistical significance of the correlation between each of the baseline variables and the time to complete remission of disease. The following baseline characteristics are considered:

[figure not shown]
- Demographic characteristics
- Comorbidities
- Tumour data
- Prior nephrectomy in the treatment of metastatic renal cancer
- Classification of the risk group according to Motzer and/or Heng criteria.
- Patient's baseline status, including ECOG grade, presence of anaemia, corrected calcium, LDH levels, neutrophil and platelet levels.

This analysis will establish which baseline characteristics are associated with a shorter complete response time to treatment.

As part of the secondary objectives, the doses and treatment regimens observed in the sample will also be descriptively summarised by means of absolute and relative frequencies. In the case of changes in the treatment dose, the frequency of patients with dose increase, dose reduction and changes in the rest regimen will be specified. Similarly, the most frequent reasons for changes in dosage and/or treatment regimen to RC will be reported.

Frequencies of the type of treatment received will be presented, depending on whether it

Pfizer Confidential

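### Requiring CR by 30 October 2018 right-truncates time to CR: the median is modestly short, and any feature that became commoner over the years can falsely appear to speed response

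*SAP*

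**What the plan says.** SAP 4.1.1 admits adults treated with first-line sunitinib "between 2007 and October 30, 2018 and have obtained, as best response to treatment, total disease remission". SAP 4.1.2 then excludes "Patients who achieved complete remission after October 30, 2018", and Protocol 8.2.2 has the same rule. The Protocol abstract dates the observation window "between June 2007 - 30 October 2018".

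For the analysis, SAP 7.2.4 says that "the Kaplan-Meier method will be used to estimate the median time to CR together with its 95% confidence interval". It justifies this by skewed times and unequal follow-up, and interprets the result thus: "The median will indicate when complete remission of the disease occurred in 50% of patients". The same section plans log-rank tests of baseline characteristics against time to CR. It also plans a multivariate Cox model that adds dose and regimen, and type of treatment (sunitinib alone or with local treatment). It states that this information will support treatment recommendations. SAP 3.2 sets significance at p<0.05.

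Neither document plans a truncation method, a minimum time since start, or stratification by start date. Protocol 8.9 lists only the uncertain number of cases and missing data as limitations.

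**The concern.** Starts are allowed up to the date by which CR must have been reached. Someone who started in 2008 could take ten years to respond and still be registered; someone who started in late 2017 had to respond within about a year. Slow responders among recent starters are therefore absent altogether, rather than present as censored observations. Kaplan-Meier handles censoring. Here nothing is censored for time to CR, so it has nothing to correct. SAP section 2 itself notes that late responders exist.

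Two results are exposed. The median time to CR is pulled downwards. And because observed times shorten as the start date approaches the cut-off, any covariate that became more frequent over the years is tied to shorter observed times even if it has no effect. The log-rank and Cox analyses would then report a spurious association in one direction, and the SAP intends to build recommendations on those analyses.

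**Working it through.** The plan has no calculation to reproduce: the figure of about 90 patients is a feasibility estimate (Protocol 8.5, SAP 4.1).

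**Inputs from the documents.** Window June 2007 to 30 October 2018: 11 × 12 + 5 = 137 months. Cited times to CR (SAP section 2): median 10.1 months in the Czech registry; in the single-hospital series of 64 CR patients, 12.6 months with drug alone (range 2–28) and 18.5 months with added local treatment (range 5–45).

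**Assumptions not in the documents.** Time to CR, T, is independent of start date and lognormal with log-SD 0.6–0.8. Time from start to cut-off, U, is uniform over 137 months.

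**1. Observed median.** A patient enters only if T ≤ U, so the observed density is proportional to f(t) × P(U ≥ t) = f(t) × (137 − t)/137. Solving for its median, and taking the sampling error of a lognormal median as SE ≈ 1.253 × log-SD × median / √90 (for example 1.253 × 0.6 × 12.6 / 9.49 = 1.0):

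| True median | Observed (log-SD 0.6 / 0.8) | Bias, months | SE at N=90 |
|---|---|---|---|
| 10.1 | 9.8 / 9.5 | −0.3 / −0.6 | 0.8 / 1.1 |
| 12.6 | 12.1 / 11.6 | −0.5 / −1.0 | 1.0 / 1.3 |
| 18.5 | 17.4 / 16.4 | −1.1 / −2.1 | 1.5 / 2.0 |

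**2. Other shapes and start patterns.** With exponential, Weibull and wider lognormal times, and with starts falling, rising or peaking, the bias was always negative: −0.1 to −3.0 months for true medians of 10.1–12.6, and −0.4 to −6.0 for 18.5. It is smallest when starts decline towards 2018 and largest when they rise.

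**3. Recent starters.** Among starts in the last 24 months, a true 12.6 is seen as 7.7–9.1 and a true 18.5 as 9.4–11.3. These patients are about 8.5% of those included (0.085 × 90 ≈ 8) and about 6% (0.06 × 90 ≈ 5) respectively.

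**4. Association tests.** Samples of 90 were simulated with a binary feature that has no effect on time to CR. It was tested by log-rank, which equals the score test of a one-covariate Cox model, at two-sided 5%:

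- Feature unrelated to calendar time: 5–6% significant.
- Prevalence rising linearly from 10% to 90% over the window: 8–14%.
- Prevalence stepping from 10% to 80% in the last 58 months: 13% to 32–33%.

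Nearly all the excess pointed the same way: the newer practice looked faster. Stratifying by calendar period of start (cuts at 24, 48, 72 and 96 months before the cut-off) brought the rate back to 5–6%.

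**5. Remedies for the median, N=90, uniform starts.**

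- The reverse-time product-limit (Lynden-Bell) estimator gave 12.6 for a true 12.6 (naive 12.1 and 11.7) and 18.3–18.4 for a true 18.5 (naive 17.3 and 16.3). At log-SD 1.0 it became unstable: its SD was 4.5 months for a true 12.6.
- Restriction to starts at least 45 months before the cut-off removes most of the bias and keeps 75–79% of patients, but total error (RMSE, naive v restricted) hardly improves: 1.04 v 1.16 and 1.50 v 1.53 for a true 12.6; 1.71 v 1.66 and 2.60 v 2.13 for a true 18.5.
- Dropping the exclusion alone moves the truncation only about 9 months, to the end of case collection on 31 July 2019 (Protocol 8.5). A true 12.6 is then seen as 11.7–12.2.

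**The case against.** The strongest reply is that the registry is descriptive and sets no hypothesis (SAP 3.1). As a summary of CRs reached by the cut-off, the sample median is correct; it is biased only when generalised to all who will respond. This stands, and is why a label is part of the fix. It does not cover the association analyses, which use p<0.05 and hazard ratios and feed recommendations.

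The second reply is size: the bias in the median is no larger than sampling error under the central assumptions, and the assumed spread may be too wide. With log-SD 0.6 or 0.8, about 3 or 6 of the 36 drug-only cases in the cited series should exceed 28 months, yet none did; at log-SD 0.4–0.5 the bias is only 0.2–0.35 months. This also largely stands, except that the cited series may itself be truncated.

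A reader might infer more than the documents support:

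- That the reported median will be badly wrong. The striking values for recent starters describe only about 6–9% of included patients.
- That local treatment technique will look falsely fast. Technique is only tabulated and enters neither test. Regimen and type of treatment enter the Cox model only; the log-rank list holds baseline characteristics.
- That a spurious association will occur. The documents show no calendar trend in any tested variable.
- That the exclusion is the sole cause. A registry of CR cases only would be truncated at data collection anyway.

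**Conclusion.** The point holds in a limited form. Time to CR is right-truncated by design, and neither Kaplan-Meier nor the unstratified log-rank and Cox analyses correct for it. Under uniform starts and log-SD 0.6–0.8, the median is short by about 0.5–1.0 months for a true 12.6 and 1.1–2.1 months for a true 18.5, which is below or about equal to the standard error with 90 patients. It could be larger if starts rose towards 2018 or times are more dispersed.

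The more consequential effect is conditional: if a tested baseline feature, the regimen or the treatment type became commoner over the years, its false-positive rate could rise from 5% to about 8–32%, in the direction of faster response. The documents do not say whether any did. This is worth correcting before analysis because the correction is cheap; it does not undermine the registry.

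**What to change.** In SAP 7.2.4:

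1. Stratify the time-to-CR log-rank and Cox analyses by calendar period of sunitinib start, with the periods fixed in advance. The start date is already collected (SAP section 5).
2. Report a right-truncation (reverse-time product-limit) median with its confidence interval beside the naive one. As a sensitivity analysis only, repeat the naive median in patients who started at least 45 months before the cut-off (by 30 January 2015); 45 months is the longest time to CR in the cited single-hospital series.
3. Describe the naive median as time to CR among CRs reached by 30 October 2018, and list the truncation as a limitation.
4. State which scan date is compared with the cut-off. SAP section 5 runs time to CR "until the day the complete response is documented in the first CT scan without lesions", whereas 7.2.4 ends it at the second, confirming scan. The two must be reconciled.

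No new data are needed. The costs are some extra programming, slightly less precision from stratifying, possible instability of the reverse-time estimate if times are widely spread, and about 20–25% fewer patients in the sensitivity analysis.
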